6.0 Blinding and Quality Assurance

A blinded assessor will collect all BBAT, BSES-SF and VAS data. The treating osteopath will be blinded to this data during the trial but will not be blinded to the medical history, consent form or treatment effects during the trial.

The blinded assessor will transfer all BBAT, BSES-SF and VAS scores into an Excel spreadsheet which will be stored in a password protected file on the CI's laptop and backed up on Southern Cross University's secure storage system. A copy of the data will be sent to a different member of the research team (RE) for quality assurance and data cleansing.

7.0 Sample Size and Statistical Power Calculation

An *a priori* sample size calculation was performed using existing data on the BBAT. With 2 Groups, a standard deviation of 2, a minimum clinically important difference (MCID) of 1.5, [52] an Alpha of 0.05 and power set at 80%, the minimum group size was calculated to be 31, giving a total sample size of 62. Allowing for a 10% drop-out rate means a total sample size of 70 is required.

8.0 Participant recruitment strategies - Posters/advertisements/electronic notices

Posters/advertisements/electronic notices advertising the trial will be placed at maternal health centres, breastfeeding drop-in centres, and private osteopathic and IBCLC clinics (Appendix 10.1) in metropolitan Melbourne and Canberra. They will direct interested mothers to contact the trial coordinator. To reduce the risk of coercion, potential participants will not be directly approached at these centres. Mothers who contact the trial coordinator will receive a copy of the participant information sheet (Appendix 5.1) and instructions on how to book a pre-screening appointment.

If the MID meets all the inclusion criteria and is deemed suitable to participate in the trial, the mother will be asked to complete the participant consent form. The mother can withdraw her infant from the trial at any time without having to give a reason for the withdrawal.

9.0 Information and consent

The information sheets (Appendix 2.1 and 5.1) and consent forms (Appendices 3.1 and 6.1) for provide clear communication and informed decision-making and prioritises the well-being and autonomy of the parents and infants throughout the process.

10.0 Risks

The risks associated with participation in this study are around the potential for physical harm to a member of a vulnerable population, psychological harm to the mother, and familial distress.

Physical harm to a member of a vulnerable population

Participation in this research carries a risk associated with harm and/or discomfort to an infant resulting from IBCLC and/or osteopathic intervention (OMT).

While the literature shows that OMT intervention has the potential to benefit infants experiencing breastfeeding difficulty,[58] there have been no reports of any adverse events associated with manual therapy intervention on infants with breastfeeding difficulty.[59, 60] This suggests that manual therapy administered by an osteopath is a relatively low-risk intervention for this group of patients.

Psychological harm to the mother

Living with an infant experiencing breastfeeding difficulty can be a distressing situation. Maternal distress can be compounded by inadequate familial support, exhaustion and feelings of failure. This may increase familial distress. Breastfeeding difficulty has also been linked to post-natal depression (PND) in a both a positive and negative way. For some women, breastfeeding helps to reduce the chance of PND or shorten how long it lasts. For others, it is the cause of stress and anxiety and can lead to a situation where discontinuing breastfeeding may be the most appropriate course of action to take under the circumstances. To monitor signs of PND or distress the practitioners (IBCLCs and osteopaths) will have access to the Edenborough Postnatal Depression Scale (EPDS) (Appendix 11.1). This 10-item self-reported measure is designed to screen women for symptoms of emotional distress during pregnancy and the postnatal period. If a clinician suspects that a mother is distressed, they will utilise this scale to monitor the level of maternal distress weekly (EPDS refers to the past 7 days). If the mother has a score of >12 on the EPDS, she will be referred to Perinatal Anxiety & Depression Australia (PANDA <https://panda.org.au>) and/or her GP.

Managing incidents of abuse

The IBCLCs, osteopaths and CI who work on the trial are registered/certified health practitioners. It is standard practice and a mandatory requirement for all registered/certified health practitioners in Australia to report any abuse and/or neglect of children to the appropriate authorities.

10.1 Risk Management

The risks associated with participation in this study will be mitigated and managed along the following lines:

Physical harm to a member of a vulnerable population

In conjunction with the research team, the treating clinician (IBCLC or osteopath) will question parents about the occurrence of adverse events during the trial. If an adverse event requires additional medical care, the treating clinician will refer the mother and infant to a hospital or their GP, depending on which is the most appropriate course of action to take given the circumstances. The adverse event will be recorded and reported to the CI who will then take appropriate action.

Psychological harm to the mother

In conjunction with the research team, the treating clinician (IBCLC or osteopath) will monitor participating mothers for signs of post-natal depression (PND). If signs of PND become apparent, the mother will be referred to their GP for further assessment and management.

Familial distress

In conjunction with the research team, the treating clinician (IBCLC or osteopath) will monitor participating parents for signs of familial distress. If signs of familial distress become apparent, the parents will be referred to their GP for further assessment and management.

11.0 Timeframes

TIMELINE

	2023	2024				2025			
	Nov/ Dec	Jan/ March	April/ May	June/ Sep	Oct/ Dec	Jan/ March	April /June	July/ Sep	Oct/ Dec
Ethics									
Recruitment									
Intervention phase									
Data analysis									
Manuscript preparation									
Final report									

Figure 2. GANTT chart

12.0 Recruitment Duration and Study Duration

It is anticipated that the recruitment phase of the trial will be 12 months. If the target recruitment number is not reached in that time, there is provision to extend the recruitment period by a further 6

months. The entire project will run over a 2-year period (Figure 2). Each participant will be involved for a total of 8 weeks.

13.0 Participant time commitment:

The total time commitment for each participant is 330 or 360 minutes (6-6.5 hours) (See Table 1). We acknowledge that in some circumstances, there will be an inequality of 10% in the total time spent for each group. We believe this is acceptable given the nature of the trial.

	INTERVENTION	IBCLC (Minutes)	IBCLC/OMT (Minutes)
Week 0	Baseline Measurements (Face-to Face)/Paperwork (Online)	60	60
Week 1	IBCLC 1	60	60
Week 2	IBCLC 2	30	30
	OMT 1		60
Week 3	Up to 2 x 1/2-hour IBCLC Telehealth	60	
	Up to 2 x ¼ - hour IBCLC telehealth		30
	OMT 2		30
Week 4	Up to 2 x 1/2 - hour IBCLC Telehealth (as required)	60	
	OMT 3 (as required)		30
	Post Intervention paperwork (Online)	30	30
Week 8	Discharge paperwork - Follow up Phone call	30	30
	Total Minutes	330	360

Table 1: Participation for each group

- IBCLC 1 Initial Consultation with an IBCLC
- IBCLC 2 Follow-up Consultation with IBCLC
- OMT 1 Initial Consultation with an Osteopath
- OMT 2 & 3 Follow-up Consultation with Osteopath

Practitioners must also complete a 4-hour pre-trial training and a 1-hour Global Health Training Centre—Good Clinical Practice Course.

Participants will be followed up 1 month after finishing the intervention phase of the trial. At that follow-up they will be asked to complete the BSES-SF and VAS measures via email and participate in a short 5-minute telephone conversation with the trial coordinator about their current breastfeeding status.

If they are continuing to have difficulty breastfeeding and need further support, they will be referred to the Australian Breastfeeding Association where breastfeeding support counsellors are available free of charge.

15 Data Collection

15.1 Personal Data

1. Full name mother
2. Full name child
3. Mother's date of birth
4. Child's date of birth
5. Child's gender
6. Mother's contact information
7. Mother's emergency contact information

15.2 Medical History Data

1. Existing medical conditions
2. Current medications
3. Allergies
4. Surgical history
5. Family medical history
6. Immunisation history
7. Lifestyle factors
8. Previous medical history
9. Maternal mental health history
10. Pregnancy and birth medical history, including gestation, delivery information, care given, Apgar scores, birth weight, birth length, and birth head circumference.
11. Current infant weight, length and head circumference
12. Breastfeeding history
13. Breastfeeding and feeding mode
14. Breastfeeding symptoms

16 Participant withdrawal

Participants are free to withdraw from the trial at any time and for any reason. Withdrawal from the trial will not affect the ongoing care of their infant at the participating clinic but may result in standard fee-for-service charges being levied by the respective clinic on consultations provided after withdrawal from the trial.

17 Data Loss:

If a participant withdraws from the trial before completing all of the intervention sessions, any data collected up until withdrawal will be retained and used in the data analysis.

18 Bias:

The withdrawal of certain participants may introduce bias into the results if those who withdraw have different characteristics or experiences compared to those who continue. As part of this research the research team will analyse the characteristics of participants who withdraw and compare them to those who remain in the study. This analysis can help identify potential biases and inform appropriate adjustments or interpretations of the results.

19 Data Safety Monitoring Board

A data safety monitoring board (DSMB) has been established for the trial. It will meet as required (but at least on two occasions) during the trial. The DSMB will consist of the following people:

1. A Paediatrician – [name] - [name] (ACT)
2. A Paediatric Osteopath & IBCLC – [name] (Victoria)
3. An independent data analyst – [name] (NSW)

The purpose of the DSMB is to monitor the progress of a trial and to make recommendations on whether to continue, modify or stop the trial for safety or ethical reasons.

An interim analysis will be conducted at 40% recruitment (28 participants) by the statistician (PG). The results of this interim analysis will be sent to the DSMB for appraisal.

20 Data Management

Data will be housed on Southern Cross University's data storage system in accordance with the University regulations for storing medical information.

Storage:

All digital trial data will be stored on a secure, password protected University server using appropriate technical and data security measures. Prior to being uploaded onto the University's server, trial data will be stored in a password protected file on the CI's university computer. Any hard copy files related to the trial will be stored in a locked filing cabinet at the CI's private office, until it is transferred to a secure data storage system with [name] at Southern Cross University.

Access:

Access to trial data is restricted to individuals named in this document.

Disclosure:

We will obtain informed consent from participants prior to participating in the study. Research findings and publications will be presented in a manner that preserves the anonymity of participants. The Joanna Briggs [61] and CONSORT [62] guidelines checklist for RCTs will guide the reporting process.

Destruction or Archiving:

Data will be retained in accordance with the National Statement 3.1.45 and 3.1.56. Data will be stored and archived for 25 years (or until the children reach the age of 25). Data will then be destroyed according to the standard procedures for the destruction of health records at Southern Cross University.

Training for recognising, managing and reporting adverse events forms part of the practitioner pre-trial training module and is in line with current definitions of adverse events in the manual therapy setting. In this research we classify adverse events in manual therapy as one of three types: [63]

- ‘Major’ adverse event is a medium to long-term, severe and unacceptable. It requires medical treatment and is serious and distressing.
- ‘Moderate’ adverse event is medium to long-term but only moderate in severity. It may require additional medical treatment and
- ‘Mild’ adverse event is short-term, non-serious, transient, and reversible. No additional medical treatment is required to resolve it.

Treating Osteopaths and IBCLCs will manage adverse events reported within their clinical sessions by using their clinical reasoning and judgement to assess the severity of the adverse event. If the adverse event is considered minor, the osteopath or IBCLC will monitor the participant, continue to provide care and record the event in their medical file. The CI will review all medical records daily during the intervention phase of the trial. If moderate, the practitioner will report it to the CI, who will then determine the appropriate referral action in consultation with the practitioner. If a major event occurs, the practitioner will immediately refer the participant for medical care and report it to the CI.

The CI will report all major and moderate adverse events, to the research team and HREC (through the Adverse Event Report form in IRMA) within 72 hours of being notified. All mild adverse events will be reported to the HREC using the same form on IRMA. Adverse events reported outside face-to-face clinic time (e.g., via phone or email) will be managed by the CI in consultation with the practitioners in the same manner as outlined.

All adverse events that occur during the trial will be recorded, regardless of whether they are related to the trial or not (Appendix 12.1). All adverse events (mild, moderate and major will be included in the project’s annual report.

22 Dissemination of results

Results from this trial may be used in publications submitted to scientific journals. They may also be used in presentations to the breastfeeding medical community, lactation consultants, midwives, maternal health nurses and the paediatric clinician community.

- [2] Kendall-Tackett K. A new paradigm for depression in new mothers: the central role of inflammation and how breastfeeding and anti-inflammatory treatments protect maternal mental health. *International breastfeeding journal*. 2007;2(1):6-. <https://doi.org/10.1186/1746-4358-2-6>.

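### For a moderate adverse event that needs medical care, the protocol gives two referral rules that differ in who determines the referral and in its order relative to the report to the CI

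*Protocol*

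**What the plan says.** Two parts of the protocol deal with referral after an adverse event.

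**Section 10.1 (Risk Management), on physical harm.** The trigger is the need for care: "If an adverse event requires additional medical care, the treating clinician will refer the mother and infant to a hospital or their GP". The choice between hospital and GP depends on the circumstances. The section then says: "The adverse event will be recorded and reported to the CI who will then take appropriate action". No severity grade is mentioned or excluded.

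**The adverse event text between section 20 (Data Management) and section 22 (Dissemination of results).** Here the trigger is the severity grade.

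- Major: "If a major event occurs, the practitioner will immediately refer the participant for medical care and report it to the CI".
- Moderate: "If moderate, the practitioner will report it to the CI, who will then determine the appropriate referral action in consultation with the practitioner".
- Lowest grade: the practitioner monitors, continues care and records the event.

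The grade definitions just before this text refer to treatment. Of a moderate event they say: "It may require additional medical treatment and" (the sentence breaks off there in the text available). Of a mild event they say: "No additional medical treatment is required to resolve it".

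The same text adds that the CI reviews all medical records every day during the intervention phase, and that "Adverse events reported outside face-to-face clinic time (e.g., via phone or email) will be managed by the CI in consultation with the practitioners", following the same approach.

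**The concern.** One rule works from the need for care and the other from the grade. If a moderate event can need medical care, the same event meets both triggers, and a practitioner reading the whole protocol finds two instructions for it. Under section 10.1 the treating clinician refers, and the CI is then told. Under the adverse event text the practitioner first tells the CI, who then determines the referral action with the practitioner.

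The participants are infants under 6 months of age, seen at 3-5 private clinics in two cities by osteopaths and lactation consultants. The protocol says that practitioners will be trained in managing adverse events. As written, it offers that training two rules for one situation, and a practitioner could follow either and be able to point to the protocol for it.

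**Working it through.** No arithmetic applies, because the protocol gives no figure on this point. The check sets the two rules side by side for each grade and asks whether they can apply to the same event and, if so, whether they agree.

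| Grade | Can it need medical treatment? | Section 10.1 | Adverse event text | Agreement |
|---|---|---|---|---|
| Mild | No, by definition | Not triggered | Practitioner monitors, continues care, records | No conflict |
| Moderate | It may, by definition | If care is needed, the treating clinician refers; report to the CI is named afterwards | Practitioner reports to the CI, who then determines referral in consultation | Conflict when care is needed |
| Major | Yes, by definition | Treating clinician refers; report to the CI is named afterwards | Practitioner refers immediately and reports to the CI | No conflict |

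1. **Overlap.** The two rules meet where an event is correctly graded moderate and needs additional medical care. The moderate definition expressly allows this, so the overlap does not depend on a grading error.
2. **Who determines the referral.** Section 10.1 has the treating clinician make it and requires no consultation first. Its reference to working with the research team attaches to questioning parents about events, not to referral. The adverse event text has the CI determine it, with the practitioner consulted.
3. **Order.** Section 10.1 names the referral and then the report. The adverse event text names the report and then the determination of referral, and keeps the word for immediate referral to major events.
4. **Precedence.** No clause makes either part govern the other. The provision for events reported by phone or email does not settle it either, since it refers back to the same handling.

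The comparison treats the lowest grade, called mild in the definitions and minor in the handling text, as one grade.

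**The case against.** **The two parts can be read together.** Section 10.1 is a general statement in a risk summary and applies when an event does require care. The later text is the graded detail: a major event requires treatment, so the practitioner refers at once; a moderate event only may require it, so the CI and practitioner settle the matter together. This is a sensible reading and explains most of the difference. It still leaves a moderate event whose need for care is clear under both rules. The protocol does not say that the graded text governs, and if it did, section 10.1 would need a limit for moderate events.

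**Both people are involved under both rules.** This is correct. The CI determines the action in consultation with the practitioner, who is not excluded, and section 10.1 also ends with action by the CI. That narrows the difference, but the referral and its order relative to the report are still assigned differently.

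**No delay is stated.** A reader might infer that one rule has the infant referred during the session while the other holds the referral, for an unlimited time, until the CI answers. The documents do not support this. Section 10.1 gives no timing, the adverse event text does not forbid the practitioner to refer, and the daily record review limits how long a recorded event could go unseen by the CI. What the text does show is a difference in sequence.

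**Sites may behave alike in practice.** A reader might also infer that clinics will treat the same event differently. That is not shown: the training module is not available and may already settle the point.

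**The moderate definition is incomplete.** Its sentence stops after the word and. Whether this comes from the authors or from reading the PDF cannot be known, and it is not counted here as an error. The clause on treatment is complete before that word, so the overlap rests on words that are present.

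**Few events are likely.** Section 1.5.2 cites 7 per 1000 infants exposed to manual therapy, all non-serious. With 1:1 allocation of 70 dyads, 70 / 2 = 35 infants would be allocated to osteopathic care, and 35 x 7/1000 = 0.245, about a quarter of an event. This supports treating the point as modest. It is not a ceiling, because the protocol records all adverse events in both groups whether or not they are related to the trial.

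**Conclusion.** The point holds for one case: a moderate adverse event that needs additional medical care. For that case the protocol assigns the referral to the treating clinician in one place, with the report to the CI named afterwards, and to the CI in consultation with the practitioner in another, after the report. It does not say which prevails. Mild and major events are handled consistently.

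This is an internal inconsistency in a safety instruction. It has no bearing on the power or the analysis of the trial. Its size cannot be put as a number from the documents, and few events may be affected. It is worth correcting because the participants are young infants and the correction is cheap. The conclusion assumes that the visible part of the moderate definition means what it says. It makes no claim that care would be delayed or that clinics would differ. The absence of time limits for the practitioner's report or the CI's decision is missing detail, not part of the contradiction.

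**What to change.** Reconcile section 10.1 with the adverse event text after section 20 so that a single rule states, for a moderate event needing medical care:

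- who decides on referral; and
- whether referral comes before or after the report to the CI.

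Use the same rule in the practitioner pre-trial training. Which rule to adopt is a clinical decision for the sponsor and its clinical advisers, and this review takes no position on it.

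The cost is about two sentences of protocol wording and a matching line in the training material. No visits, staff or data collection are added.
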